review of the current literature, a series of important questions have emerged:

1.	What is the trajectory of caregiver resilience over the first two years postinjury? Does resilience
	change over time for some caregivers? If yes, what patient and caregiver factors are related to
	decline or improvement?
2.	What is the relationship between caregivers' resilience and their emotional well-being? Can the
	proposed longitudinal, multi-center study reproduce results from several single-center, small-
	sample studies with TBI and dementia caregivers?
3.	A few TBI caregiver studies found a relationship between caregiver resilience and perceived
	burden. In addition to perceived burden, do other caregiver factors (e.g., needs, time spent caring
	for the patient) relate to resilience?
4.	What is the relationship between caregiver resilience and patient characteristics, including
	resilience, emotional distress, and functional status?

C. Methodology

C1. Stage of Research

The proposed module project is best labeled as falling within the "Exploration and Discovery" stage of research. The present investigation is intended to generate hypotheses and theories through analysis of prospective, multi-center, longitudinal data. There is little information to aid our understanding of the construct of resilience in caregivers after TBI, despite the potential relevance to patients' rehabilitation and recovery. Research suggests that resilience can be improved with training, and we anticipate that the results of this project will facilitate the development of effective interventions that benefit caregivers and patients.

C2. Sample

Information regarding inclusion and exclusion criteria, enrollment rate, and participant incentives is provided herein. Recruitment information is provided in the *Procedure* section.

Inclusion criteria: Caregivers age 18 and older, identified within six months postinjury by TBIMS NDB participants (survivors) will be included. Participants will include relatives, friends, or other acquaintances involved in providing care, support, or other meaningful assistance to the survivor. In cases where there is more than one caregiver available, first priority will be given to the caregiver who is providing the most care to the survivor. A script will be developed for data collectors, allowing them to better identify a single caregiver for each survivor.

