Zarit Burden Interview (ZBI): The ZBI was originally developed as a 22-item questionnaire designed to quantify caregiving burden and is the most commonly used measure of such.²⁴⁴ Caregivers are asked to describe perceived changes in their emotional or physical health, social life,

and financial status as a result of caring for a relative. Items are rated on a 5-point Likert scale, ranging from 0 (never) to 4 (nearly always). A total score is derived, representing the extent of burden, with higher scores denoting greater burden. Research has evaluated the utility of a 12-item version.²⁴⁵ The correlations between the short and full version ranged from .92 - .97, substantiating the comparability of both versions. In a study among three caregiving populations (advanced cancer, dementia, and acquired brain injury), the 12-item ZBI had excellent validity (rho = .95-.97).²⁴⁶ Both the 12- and 22-item versions have been used with adult and pediatric TBI populations.^{66,219,223,247} The present investigation will utilize the 12-item version.

Caregiver demographics and history: Demographic data collected will consist of age, gender, race/ethnicity, marital status, household income, years of education, occupational status, and nature and length of relationship with survivor. To help characterize relationships, the caregiver will also be asked to indicate: (a) whether they are living with the survivor; (b) the number of hours spent caring for them daily; and (c) and the average number of days per week the caregiver sees the survivor. Additionally, information will be obtained about current and past mental health treatment and substance abuse, using the same variables as the NDB.

Survivor demographics and history: Data from the NDB protocol will be used. In addition, at the 6-month follow-up, the Disability Rating Scale and PART (Participation Assessment with Recombined Tools-Objective) will be collected.

Injury characteristics: The following information will be used from the NDB data collection: date of injury, etiology, admission GCS score, duration of unconsciousness and post-traumatic amnesia, duration of hospitalization, and history of neurosurgical intervention (e.g., craniotomy/craniectomy, ICP monitoring).

C4. Procedure

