This will be a multi-center, prospective longitudinal investigation. Newly enrolled TBIMS NDB participants will be contacted after discharge and no more than six months postinjury and asked to identify a caregiver. Caregivers will be approached, provided with information about the project, and invited to participate. Informed consent will be obtained. At six months postinjury (+/-

two weeks), caregivers will be asked to complete baseline assessment materials and TBIMS participants will complete measures as well. Caregiver participants will be contacted again at 12 and 24 months postinjury and asked to complete primary outcome measures. TBIMS participants will be contacted per standard NDB protocols. Data will be collected via telephone, in person, or by mail at the time points specified in the following table.

Content Area/Measure	6 months	12 months	24 months
Demographics (caregiver)	Х		
Functional Outcome (DRS, PART)	Х	Х	Х
Resilience (CD-RISC)	Х	Х	Х
Emotional wellbeing (PHQ-9 and GAD-7)	Х	Х	Х
Family Needs (FNQ)	Х	Х	Х
Burden (ZBI)	X	X	Х

Estimated time for caregivers to complete measures is 20-30 minutes. Additional time required of survivors, beyond the standard NDB protocol, is 10-15 minutes. Project staff will make accommodations for persons with visual, motor, and other impairments. To maintain confidentially, data collected from the caregiver will not be shared with the survivor, and data collected from the survivor will not be shared with the caregiver. The same procedures will be employed at collaborating centers.

With regard to safety monitoring at VCU, [name] will be on call during each assessment. He will monitor the status of enrolled participants and address urgent situations. When concerns arise, [name] will be contacted immediately to make a clinical decision regarding the need for further evaluation, treatment, or referral. In-person assessments will be conducted in the hospital where a full range of mental health services are available. Once collaborating centers are identified, the project will be submitted to the VCU Office of Research Subjects Protection for review and approval. More detailed information regarding human subjects protection and safety monitoring procedures is detailed in the *Human Subjects Narrative* (Form 424).

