Following our strategy with previous longitudinal studies of resilience (under review, *Archives of Physical Medicine and Rehabilitation*), individual growth curve analyses will be used to assess the relationships between caregivers' resilience and the longitudinal caregiver and patient characteristics. These models will include correlated random intercept and slope effects. Separate models will be fit with time, each caregiver and patient characteristic, and the interaction of these variables. Similar models will be fit without the interactions, and any interaction or individual

characteristic significant at the 0.05 level will be candidates to be entered into the final model. A backwards selection procedure will be performed so that all remaining characteristics have a p-value <0.05. The continuous time variable will remain in the model regardless of statistical significance. A random effect will be included to adjust for the different study sites and all inferences will be adjusted for the estimation of the random effects using a Kenward-Rogers adjustment.²⁵³

The SAS software will be used for all analyses except the LCLMM analysis, which will be performed using the 'lcmm' package in R.²⁵¹ All inferences will be made at the 0.05 level and all statistical models, with the exception of the ANOVA and Pearson chi-squared tests, are able to incorporate data that is missing at random. An adjustment for multiple comparisons will not be made due to the exploratory nature of the study.²⁵⁴

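### Caregiver module: caring time is scheduled at 6 months only, so it can be a baseline predictor of resilience but not a changing exposure at 12 and 24 months

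*Combined protocol and SAP*

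**What the plan says.** All references are to the project Caregiver Resilience: A Longitudinal Investigation.

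- **B. Research Questions.** Question 1 sets the horizon: "What is the trajectory of caregiver resilience over the first two years postinjury". It goes on to ask which patient and caregiver factors accompany decline or improvement. Question 3 asks, beyond perceived burden, "do other caregiver factors (e.g., needs, time spent caring" and so on, relate to resilience.
- **C3. Measures, Caregiver demographics and history.** This paragraph holds the only items on caring time: "To help characterize relationships, the caregiver will also be asked to indicate: (a) whether they are living with the survivor", then "the number of hours spent caring for them daily", then "the average number of days per week the caregiver sees the survivor". No time point is given for them.
- **C4. Procedure.** The table marks the caregiver demographics row at 6 months only. The rows for function (DRS, PART), resilience (CD-RISC), emotional wellbeing (PHQ-9, GAD-7), needs (FNQ) and burden (ZBI) are marked at 6, 12 and 24 months. The text agrees: "Caregiver participants will be contacted again at 12 and 24 months postinjury and asked to complete primary outcome measures".
- **D. Data Analysis.** Growth curve models are to "assess the relationships between caregivers' resilience and the longitudinal caregiver and patient characteristics", each characteristic being fitted with time and their interaction.

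**The concern.** Hours of care and co-residence may change between 6 and 24 months after the injury as survivors recover or move. Needs and burden, the other factors that question 3 mentions, can enter the growth models with a value from each visit. Caring time cannot, because it has one value per caregiver.

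Two things are at stake. First, any association between caring time and resilience at 12 or 24 months uses a value that is 6 or 18 months old. Second, the module cannot see change in caring. A rise in resilience because care has ended looks the same as a rise in someone still caring. The caregiver is identified once, within six months of injury, and then answers the needs and burden scales at every visit whether or not care continues. A low burden score at 24 months could mean lighter care or none.

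**Working it through.** **The plan's own figures.** Enrolment is 78 + 234 = 312. Two-year completers: 312 × 0.85 = 265.2, given as 266. Observations: 266 × 3 = 798. A one-way ANOVA with three groups, N = 266, alpha 0.05 and 80% power detects f = 0.191, against the stated 0.19. These reproduce, and the point below does not alter them.

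**Schedule.** Of three planned CD-RISC scores per completer, one has a caring-time value from the same visit. The other two do not: 266 × 2 = 532 of 798.

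**What staleness could cost.** The documents give no figure for the stability of caring time, so these are assumptions with a range. Let r be the correlation of resilience with hours of care at the same visit, and s the correlation of 6-month hours with hours at a later visit. Assume that 6-month hours act only through current hours. Power is from Fisher's z, n = 266, two-sided 0.05: Φ(atanh(correlation) × √263 − 1.96), with √263 = 16.22.

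*One association at 24 months (illustration; no such test is planned).* The observable correlation is r × s. With r = 0.25:

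- current hours: atanh(0.25) × 16.22 = 4.14, power 98.5%
- s = 0.7: atanh(0.175) × 16.22 = 2.87, power 82%
- s = 0.5: atanh(0.125) × 16.22 = 2.04, power 53%

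*Main effect over all three visits (closer to the planned growth model).* Use the mean of the three scores. Its correlation with 6-month hours is r × (1 + s12 + s24)/3 ÷ √((1 + 2c)/3), where c is the between-visit correlation of CD-RISC. The plan's power analysis uses c = 0.25; 0.8 is added as an unfavourable assumption. The 12-month stability s12 is either equal to s24 or follows exponential decay, s24^(1/3).

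| c | s24 | s12 | correlation at r = 0.25 | power |
|---|---|---|---|---|
| 0.25 | 0.7 | 0.70 to 0.89 | 0.283 to 0.305 | 99.7% to 99.9% |
| 0.25 | 0.5 | 0.50 to 0.79 | 0.236 to 0.270 | 97% to 99% |
| 0.8 | 0.7 | 0.70 to 0.89 | 0.215 to 0.232 | 94% to 97% |
| 0.8 | 0.5 | 0.50 to 0.79 | 0.179 to 0.205 | 84% to 92% |

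With fully stable hours (s = 1) and c = 0.8, the correlation is 0.25/0.931 = 0.269 and power is 99.4%. The worst row is therefore a fall from about 99% to 84%.

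The result depends on r. At r = 0.171, the smallest single-visit correlation that 266 caregivers detect with 80% power, the worst combination (c = 0.8, s = 0.5 at both visits) gives 0.171 × 0.667/0.931 = 0.122 and 51%, against 85% with s = 1.

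*Change in caring.* With one value per person, no change score exists. The association of change in hours with change in resilience cannot be estimated at any sample size.

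**The case against.** The strongest reply is that this is a choice of design and not a contradiction. Question 3 names no time point and does not ask for a concurrent exposure; the two-year horizon comes from question 1, the CD-RISC schedule and the growth models. A 6-month value is a legitimate predictor of later trajectory. The longitudinal characteristics in the analysis plan are already supplied by the repeated scales. The module is labelled exploratory, and time spent caring is one example in a parenthesis. All of that stands, and it limits the weight of the point.

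It can also be said that no sentence rules out repeating the items, and that the table is a summary with no separate row for them. This too is fair: 6 months only is inferred from the paragraph in which the items sit and from the schedule row. But text and table agree, and nothing schedules a repeat, so staff who follow the plan as written would not collect the data.

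A reader might infer three stronger things that the documents do not support:

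- **That power for question 3 falls to 82% or 53%.** Those figures belong to a single 24-month correlation that is not planned.
- **That people who have stopped caring cannot be identified at all.** Survivors are followed under National Database protocols that are not set out here and might carry indirect information on living situation. What is missing is a scheduled caregiver item.
- **That the change is free of regulatory cost because the module had not gone to the IRB.** That is grant-stage text. The work plan puts IRB submission in months 1-6 and enrolment in months 1-36. Budget Year 3 starts on 10/1/2019, so month 1 is October 2017 and month 36 is September 2020, while the same file lists documents dated May 2021.

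**Conclusion.** The point holds in a limited form. As scheduled, caring time is a baseline predictor only. It cannot be a visit-level characteristic in the growth models, it cannot be related as a change to the decline or improvement in question 1, and the scheduled caregiver data do not show whether care continues.

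The size depends on the stability of caring time. For the three-visit main effect the loss is little to moderate under the assumptions r = 0.25 and 24-month stability of 0.5 to 0.7, and larger if the true association is weaker. Associations specific to 12 or 24 months are attenuated in proportion to stability, to 70% or 50% of their size in these examples. Associations with change in caring are lost entirely. All of this assumes that earlier hours matter only through current hours. Nothing here touches the randomised comparison of RAI and RAI+.

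**What to change.** Add a row to the C4 schedule so that the three caregiving items, and one question on whether the respondent is still giving care, are asked at 6, 12 and 24 months. Enter them in the growth models as time-varying characteristics and keep the 6-month value as a separate baseline predictor. Since eligibility covers support and other assistance as well as care, define in the implementation manual what counts as still giving care.

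Any analysis limited to visits where care continues should be reported as a descriptive sensitivity analysis only. It conditions on a state that arises after baseline and may itself be related to resilience, so it can introduce selection.

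The cost is a minute or two at two existing contacts, against a caregiver assessment of 20-30 minutes, plus an IRB amendment if the module has already been approved. If follow-up is under way, the items can be added only for visits still to come. If none remain, state in the report that caring time was measured at 6 months and interpret it as a baseline predictor.

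### In the exploratory caregiver module, the growth-curve selection rule protects only time, so a characteristic-by-time interaction can be kept without its main effect

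*Combined protocol and SAP*

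**What the plan says.** The rule is in Caregiver Resilience: A Longitudinal Investigation, section D (Data Analysis). It has three steps.

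- Screening with interaction: "Separate models will be fit with time, each caregiver and patient characteristic, and the interaction of these variables".
- Screening without interaction, and entry: the sentence opens "Similar models will be fit without the interactions, and any interaction or individual" and, after a page break in the text, it ends "characteristic significant at the 0.05 level will be candidates to be entered into the final model".
- Removal, and protection of time: terms are eliminated backward, "so that all remaining characteristics have a p-value <0.05. The continuous time variable will remain in the model regardless of statistical significance".

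On the random part the section says: "These models will include correlated random intercept and slope effects". It does not say whether time is counted from injury or from the first visit. The Procedure section (C4) puts assessments at 6, 12 and 24 months postinjury. Research question 1 (section B) asks whether resilience changes over time and then, of a fall or a rise, puts the question that begins "If yes, what patient and caregiver factors are related to".

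**The concern.** The entry sentence lets an interaction or a characteristic qualify, each on its own p-value, and the second set of screening models judges the characteristic with no interaction present. Groups that start apart and cross have an average difference near zero. Such a characteristic fails that screen while its interaction passes. Backward selection gives a second route to the same result, because only time is exempt from removal.

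A model with time and the interaction but no main effect makes the groups identical at time zero. If time is months postinjury, that point lies outside the 6-to-24-month data. A true difference in level is then absorbed by the slope. The terms at risk describe caregiver groups whose resilience moves apart or together, which is part of what research question 1 asks.

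**Working it through.** **Inputs from the plan.** Visits at 6, 12 and 24 months; 266 caregivers completing and a correlation between time points of 0.25 (Power Analysis); 0.05 level, taken as two-sided; a 3-unit CD-RISC change as the cutoff for changing resilience (section D).

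**Assumptions.** Two equal groups. A true group difference of -1.5 points at 6 months and +1.5 at 24 months, a divergence of 3 points. No caregiver SD is given, so SD 8 is used with the 0.25 correlation; the nearest figure in the plan is the survivor baseline SD of 8.1. A second covariance has random intercept SD 6, slope SD 0.15 per month, correlation between them -0.2 and residual SD 3.5. It implies a 6-to-24-month correlation of about 0.67 and a change SD of 5.6.

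The plan gives no figure for this rule, so there is none to reproduce.

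**Step 1: text check.** Section D has no sentence tying a characteristic to its interaction, and time is the only term it forces in.

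**Step 2: effect of dropping the main effect.** Let Y = b0 + b1·t + b2·X + b3·X·t. Refitting without X gives an expected interaction of b3 + b2·k, where k = (t'V⁻¹1)/(t'V⁻¹t). With equal correlation ρ, V⁻¹ is proportional to I - cJ with c = ρ/(1+2ρ), and the SD cancels. For ρ = 0.25, c = 0.25/1.5 = 1/6.

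*Months postinjury, t = (6, 12, 24):*
- Σt = 42 and Σt² = 756, so k = 42(1 - 3/6)/(756 - 42²/6) = 21/462 = 1/22.
- b3 = 3/18 = 0.1667 and b2 = -1.5 - 6 × 0.1667 = -2.5.
- Fitted slope = 0.1667 - 2.5/22 = 0.0530 per month.
- 18-month divergence = 18 × 0.0530 = 0.95 (true 3.0).
- 6-month difference = 6 × 0.0530 = +0.32 (true -1.5).

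*Time from the 6-month visit, t = (0, 6, 18):*
- k = 24(1 - 3/6)/(360 - 24²/6) = 12/264 = 1/22, and b2 = -1.5.
- Fitted slope = 0.1667 - 1.5/22 = 0.0985 per month.
- Divergence = 18 × 0.0985 = 1.77 (true 3.0). The 6-month difference is exactly 0.

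Under the second covariance with months postinjury, the fitted divergence is about 2.0, the 6-month difference about +0.7 and the 24-month difference about +2.6 (true +1.5).

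The error need not be an understatement. For a difference of +1 growing to +4, with ρ = 0.25 and time from the 6-month visit, the slope becomes 0.1667 + 1/22 = 0.212, which is too large. With months postinjury the same pattern has b2 = 1 - 6 × 0.1667 = 0 and no expected bias. The result therefore depends on an origin that the plan leaves open.

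**Step 3: how often.** The rule was simulated with known covariance and z-tests at 0.05, for the -1.5 to +1.5 crossing in months postinjury. On the first reading the main effect must qualify in the no-interaction model. On the second it enters with its interaction and is then tested at 0.05.

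| | Correlation about 0.67 | Correlation 0.25, SD 8 |
|---|---|---|
| First reading: interaction qualifies, main effect does not | 91% | 68% |
| of all runs, kept without main effect | 88% | 25% |
| of all runs, interaction then lost | about 3% | 43% |
| Second reading: kept without main effect | 19% | 10% |

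In the 88% of runs, the mean divergence was 2.1, against 3.1 when the main effect was kept in the same runs.

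**The case against.** The strongest reply is that the plan is silent on hierarchy and does not reject it. The removal sentence speaks of characteristics, just after the text has distinguished them from interactions, and each interaction is first estimated in a model that contains its main effect. An analyst might carry the main effect along without being told. That is fair, and it is why the second reading is shown. But on that reading the main effect can still be removed at 0.05, because only time is exempt.

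It is also fair that a crossing symmetric about zero is the case most likely to fail the main-effect screen, that 0.67 is not the plan's correlation, and that the frequencies fall sharply when either the reading or the correlation changes. All of this stands, and it limits how firmly any single percentage can be quoted.

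Scope is limited too. The module is labelled exploratory and hypothesis-generating, and section D waives multiplicity adjustment on that ground. The waiver concerns how many tests are run. It gives no reason to fit a mean model that forces groups together at an arbitrary time. The plan also examines change through ANOVA and chi-square tests and through a latent-class model, none of which uses this rule, so research question 1 does not rest on these interactions alone.

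**Conclusion.** The point holds as a defect in a stated rule. Followed as written, it can leave an interaction without its main effect. For the crossing examined, it then cuts a 3-point divergence to between about 1 and 2 points in months postinjury, or loses the interaction. How often this happens, from about 10% to 88% here, depends on the reading, the correlation, the assumed SD and the assumed pattern. There is no bias where the true difference at the time origin is zero.

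Four stronger conclusions might be inferred, and the documents do not support them.

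- That the 6-month difference is always reversed. Reversal needs an origin other than the 6-month visit; with that origin the difference is erased instead.
- That the failure is nearly certain. This is close to true only on the first reading with the higher correlation and a crossing pattern.
- That a constant difference would routinely appear as divergence. A truly null interaction must first pass 0.05 in a model containing its main effect, which limits this to about 5% per characteristic.
- That the trial is affected. The RAI/RAI+ hypotheses use a separate, prespecified mixed model with no such selection.

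**What to change.** Add one sentence to section D of the caregiver module: any characteristic whose interaction with time is a candidate or is retained stays in the model regardless of its own p-value. The cost is about one degree of freedom per retained interaction for a binary or continuous characteristic, and more for one with several levels. No new data are needed.

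Stating the time origin, for example the 6-month visit, is optional. Once main effects are kept, the fitted slopes and differences no longer depend on the origin, and the choice only makes the main effect easier to interpret.
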